6.7.2. Laboratory Data

Safety laboratory data will be summarized according to Pfizer standards for each phase.

6.7.3. Vital Signs

Descriptive summary tables will be provided in accordance with Pfizer reporting standards for each phase.

6.7.4. Physical Examination

Descriptive summary tables will be provided in accordance with Pfizer reporting standards for each phase.

6.7.5. ECG

ECG data at screening and Week 48/end of study, change from screening to Week 48/end of study, number (%) of subjects with any clinically significant changes will will be descriptively summarized by treatment group in double-blind phase and for FAS-DB.

CCI

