6.2.7. Visit 6 (End of Study Visit; Week 48; Day 336/Early Withdrawal Visit)

Subjects who did not achieve LDA at Week 24 and were therefore not randomized do not require a separate EOS visit except for QuantiFERON Gold[®]™ In-Tube Test.

There is a ±10 day window for this visit. Subjects are required to fast for 6 hours prior to the visit. Procedures to be performed at Visit 6 include:

- Complete Physical Examination: height, weight, vital signs, general appearance, skin (presence of rash or suspicious lesions), HEENT (head, eyes, ears, nose and throat), lungs (auscultation), heart (auscultation for presence of murmurs, gallops, rubs), lower extremities (peripheral edema), abdominal (palpation and auscultation), neurologic (mental status, station, gait, reflexes, motor and sensory function, coordination) and lymph nodes.
- Laboratory testing including blood chemistry, hematology, CRP, lipid profile (fasting), ESR.
- 12-lead electrocardiogram.
- Biospecimen collection for banking.
- Pregnancy testing must be completed for all women of childbearing potential: all subjects must test negative; confirmation and documentation of the use of 2 highly effective methods of contraception by subjects of childbearing potential or their

partners must be done. For contraception and reproductive status details to be applied in Belgium, Czech Republic, Germany, Hungary, Italy, Poland, Spain, and the United Kingdom see [Appendix 7](#).

- 28 tender /painful and swollen joint counts.
- Completion of the following assessments:
 - Subject assessment of arthritis pain.
 - Subject global assessment of arthritis.
 - Physician global assessment of arthritis.
 - HAQ DI.
 - SF 36 (Version 2, Acute).
 - EuroQol EQ 5D.
 - WPAI Questionnaire.
 - FACIT Fatigue Scale.
 - US and Canada ONLY: RAPID3.
- Safety Assessment and AE reporting.
- Assess safety events for adjudication by the appropriate adjudication or review committee and collect biopsies of potential malignancy events for central laboratory pathologist over read and report to Pfizer Study Team or designee.
- Concomitant Medication Review.
- Review of dosing diary with the subject (the diary will be returned at this visit).
- Return unused investigational products.

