7.4. Electrocardiogram

A 12-lead electrocardiogram (ECG) will be obtained on all subjects at the Screening Visit and at the End of Study visit. All ECGs should be performed after the subject has rested quietly for at least 10 minutes. ECGs will be read locally. All ECG results will be documented in the CRF and copies of the tracings maintained in the subject's source documentation. Subjects with a screening 12-lead electrocardiogram that demonstrates clinically significant abnormalities requiring urgent treatment (eg, acute myocardial infarction, serious tachy- or bradyarrhythmias) or that is indicative of serious underlying heart disease (eg, cardiomyopathy, major congenital heart disease, low voltage in all leads) should not be enrolled in the study.

End of Study ECGs will be compared to the Screening ECG and any clinically significant changes will be recorded as adverse events, and evaluated further, as clinically warranted.

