9.5. Safety Analysis

The safety analysis set is defined as those subjects who received at least one dose of tofacitinib MR 11mg QD with MTX at entry into the study. All displays of safety data will be separated by the open-label phase and the double-blind phase.

CCI [REDACTED]

[REDACTED]

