4. ANALYSIS SETS

4.1. Full Analysis Set

There are two full analysis sets, one is for open-label run-in phase and one is for double-blind MTX withdrawal phase.

- **Open-Label Period Full Analysis Set (FAS-OL)**

FAS-OL includes all subjects who received at least one dose of tofacitinib MR 11mg plus MTX during open-label phase.

- **Double-Blind Period Full Analysis Set (FAS-DB)**

FAS-DB includes all subjects who received at least one dose of tofacitinib MR 11mg plus MTX during the open-label run-in phase, and were randomized and received at least one dose of the randomized investigational drug regimen (tofacitinib MR 11mg with MTX or tofacitinib MR 11mg with placebo for MTX) during the blinded MTX withdrawal phase.

A randomized but not treated subject, or treated but not randomized subject during MTX withdrawal phase will be excluded from FAS-DB.

A subjects who was randomized but took incorrect treatment during MTX withdrawal phase will be reported under the randomized treatment group for all efficacy analyses.

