4.3. Safety Analysis Set

There are three safety analysis sets, two for two study phases (open-label run-in phase and double-blind MTX withdrawal phase) and one for overall study period.

- **Open-Label Run-in Phase Safety Analysis Set (Safety-OL)**

Safety-OL will include all subjects who received at least one dose of tofacitinib MR 11mg QD plus MTX during open-label run-in period. It is same as FAS-OL.

- **Double-Blind MTX Withdrawal Phase Safety Analysis Set (Safety-DB)**

Safety-DB will include all subjects who received at least one dose of study drug (tofacitinib MR 11mg QD with blinded MTX or tofacitinib MR 11mg QD with blinded matching placebo for MTX) during double-blind MTX withdrawal phase.

- **Overall Study Safety Analysis Set (Safety-All)**

Safety-All consists of all subjects who received at least one dose of study drug during the study.

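### SAP 6.7.5 summarizes ECGs only for FAS-DB, so no visible table shows the ECG change from screening of subjects who withdraw during the run-in

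*SAP*

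**What the plan says.** **Collection.** Protocol 7.4 states: "A 12-lead electrocardiogram (ECG) will be obtained on all subjects at the Screening Visit and at the End of Study visit". Results go into the CRF, the final tracing is compared with screening, and clinically significant changes become adverse events. The final ECG belongs to "Visit 6 (End of Study Visit; Week 48; Day 336/Early Withdrawal Visit", so the visit serves both those who complete and those who leave early; Protocol 6.2.7 and the Schedule of Activities both list the ECG there. Footnote k of the Schedule waives a separate final visit, apart from the tuberculosis test, only for subjects who miss low disease activity (LDA) at Week 24.

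**Analysis.** Protocol 9.5 defines the safety set as "those subjects who received at least one dose of tofacitinib MR 11mg QD with MTX at entry into the study" and adds: "All displays of safety data will be separated by the open-label phase and the double-blind phase". SAP 4.3 provides matching sets for the run-in (Safety-OL), the double-blind phase (Safety-DB) and the whole study (Safety-All). SAP 6.7.1 to 6.7.4 report adverse events, laboratory data, vital signs and physical examination for each phase. SAP 6.7.5 instead has ECG data "descriptively summarized by treatment group in double-blind phase and for FAS-DB". SAP 4.1 limits FAS-DB to subjects who took open-label treatment and "were randomized and received at least one dose of the randomized investigational drug regimen".

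**The concern.** ECG is the one item in SAP 6.7 tied to a full analysis set rather than reported by phase, and the SAP gives no reason. Its version history records only that an ECG summary was added.

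The omitted group is not random. FAS-DB members completed 24 weeks of tofacitinib plus methotrexate, reached CDAI of 10 or less, were randomized and were dosed again. Those who left earlier include anyone withdrawn for a safety reason listed in Protocol 7.23. Protocol 1.2.1 names cardiovascular disease among findings in RA subjects receiving tofacitinib, and Protocol 9.8 sets up a cardiovascular adjudication committee. An ECG table without the early leavers describes only subjects who tolerated and responded to the combination. At stake is the completeness of a descriptive safety display, not the non-inferiority conclusion.

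**Working it through.** **Step 1: who can be in the ECG table.**

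| Group | Final ECG due? | In protocol safety set? | Can be in FAS-DB? |
|---|---|---|---|
| Withdrew during run-in | Yes (Visit 6 as early withdrawal visit) | Yes | No |
| Completed run-in, no LDA at Week 24 | None scheduled (footnote k; no ECG at Visit 4) | Yes | No |
| Randomized and dosed in double-blind phase | Yes | Yes | Yes |

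Only the first row has ECGs that are due but fall outside the table.

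**Step 2: reproduce the planning figures.** Inputs from Protocol 9.1: 680 enrolled, 15% run-in discontinuation, 40% LDA at Week 24, 232 randomized.

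- Enrollment needed = 232 / 0.40 / 0.85 = 682.4, against 680 stated.
- Expected randomized = 680 × 0.85 × 0.40 = 231.2, against 232 stated.

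The planning figures reproduce within rounding.

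**Step 3: size of the first row.** Taking all enrolled subjects as dosed:

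- Run-in withdrawals = 680 × 0.15 = 102, or 15% of those dosed.
- This does not depend on the LDA rate. At the interim rate of about 79% (Protocol Section 3), the number randomized would be 680 × 0.85 × 0.79 = about 457, and the withdrawals would still be 102.

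**Step 4: why 102 is an upper bound at the planned rate.**

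- Protocol 6.3 asks withdrawing subjects to return for a final visit where applicable; not all will.
- The amendment summary shows that a 2016 administrative letter had removed the end-of-study ECG from Protocol 7.4, and that Amendment 2 (December 2017) settled on keeping it and added it to the Schedule and to Protocol 6.2.7. Half the study was enrolled by 02 August 2017, so some earlier withdrawals may have had no final ECG.

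**Step 5: the group that does not count.** Subjects without LDA number 680 × 0.85 × 0.60 = about 347 at the planned rate, or 680 × 0.85 × 0.21 = about 121 at the interim rate. They are outside FAS-DB too, but have no final ECG scheduled. The total outside FAS-DB, 680 − 232 = 448, therefore overstates the untabulated ECGs.

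**The case against.** **Redaction.** A reader might infer that these ECGs are never tabulated. The documents do not support that. The text directly after SAP 6.7.5 is redacted, and the version history says Section 7 concerns analysis of the open-label phase. It could contain an ECG display. This stands: the claim is limited to the visible tables.

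**Adverse event route.** Clinically significant changes must be recorded as adverse events (Protocol 7.4), and these are summarized for each phase (SAP 6.7.1), with Safety-OL available as denominator. ECGs are read locally, so the clinically significant count in SAP 6.7.5 appears to rest on the same site judgement. This largely stands. It does not supply the ECG values, the change from screening, or the number of leavers with paired ECGs, so a reader cannot tell few findings from few tracings.

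**Conflict with the protocol.** A reader might infer a breach of the protocol. That is too strong. Protocol 9.5 can be read as separating whatever displays are made, without requiring a table for every parameter in both phases. ECG is not among the safety endpoints in Protocol 2.2.1.4. The SAP may modify the protocol's plans, and only major changes to the primary endpoint or its analysis need an amendment. This is an unexplained departure, not a forbidden one.

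**Schedule.** ECGs are taken only at screening and Visit 6, unlike vital signs, so run-in completers have no Week 24 ECG and an open-label table would hold early withdrawals alone. This stands and governs how the table must be labelled; it does not justify leaving the table out.

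**Choice of set.** FAS-DB and Safety-DB both require a double-blind dose and differ essentially only in subjects treated without being randomized. That part of the fix serves consistency and may change no number.

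**Conclusion.** The point holds as a minor gap in safety reporting. The population rule in SAP 6.7.5 drops ECG data that the protocol collects on early leavers. It departs without explanation from the protocol's safety set and from how the SAP treats its other safety data.

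The size is at most about 102 of 680 subjects (15%), assuming that the planned discontinuation rate holds, that all enrolled subjects are dosed, and that every run-in withdrawal has a final ECG. The true number will be lower. It also assumes that the redacted section holds no open-label ECG display.

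A reader might infer that the reported rate of ECG change is biased downward by a calculable amount. The documents give no ECG event rates in either group, so neither the size nor the direction of a difference can be shown; a higher rate among leavers is plausible but assumed. The primary analysis is unaffected.

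**What to change.** In SAP 6.7.5:

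1. Add a descriptive summary of ECG change from screening, with the number and percentage showing clinically significant change, for Safety-OL subjects who withdrew in the run-in and have both ECGs. State that denominator and label the table as early withdrawals only, because it does not estimate a rate for all dosed subjects.
2. Use Safety-DB in place of FAS-DB for the double-blind table.

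If the redacted Section 7 already contains the first item, a cross-reference from SAP 6.7.5 is enough. Separately, the all-subjects statement in Protocol 7.4 should be reconciled with footnote k, under which Week 24 subjects without LDA have no final ECG scheduled.

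The cost is one extra descriptive table from data already collected, with no new procedure and no change to the primary analysis.

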9. APPENDICES

Appendix 1. DATA DERIVATION DETAILS

Appendix 1.1. Endpoints Definition and Derivation

Endpoint	Defination/Calculation
DAS28-4 (CRP)	$0.56*\sqrt{(TJC28)} + 0.28*\sqrt{(SJC28)} + 0.36*\ln(\text{CRP in mg/l} + 1) + 0.014*\text{PtGA in mm} + 0.96$
DAS28-4 (ESR)	$0.56*\sqrt{(TJC28)} + 0.28*\sqrt{(SJC28)} + 0.70*\ln(\text{ESR in mm/ hour}) + 0.014*\text{PtGA in mm}$
SDAI	$(28TJC) + (28SJC) + [\text{PhyGA in cm}] + [\text{PtGA in cm}] + [\text{CRP in mg/dL}]$
CDAI	$(28TJC) + (28SJC) + [\text{PhyGA in cm}] + [\text{PtGA in cm}]$
ACR20/50/70 responder	ACR20: at least 20% improvement in tender and swollen joint counts and at least 20% improvement in at least 3 of the 5 remaining ACR-core set measures: subject and physician global assessments, pain, HAQ-DI, and CRP. Similarly, ACR50 and 70 are calculated with the respective percent improvements.
ACR/EULAR Boolean-based definition of remission	all of the following satisfied: $TJC \leq 1$, $SJC \leq 1$, $CRP \leq 1$ mg/dL, $PtGA \leq 1$ on a 0-10 scale
LDA of DAS28-4 (CRP)	$DAS28-4 (CRP) \leq 3.2$
LDA of DAS28-4 (ESR)	$DAS28-4 (ESR) \leq 3.2$
LDA of SDAI	$SDAI \leq 11$
LDA of CDAI	$CDAI \leq 10$
Remission of DAS28-4 (CRP)	$DAS28-4 (CRP) < 2.6$
Remission of DAS28-4 (ESR)	$DAS28-4 (ESR) < 2.6$
Remission of SDAI	$SDAI \leq 3.3$
Remission of CDAI	$CDAI \leq 2.8$
HAQ-DI responder	Decrease ≥ 0.22
RAPID3	$(\text{HAQ} * 3.33 + \text{pain VAS in mm/10} + \text{PtGA in mm/10})/3$.

TJC = tender joint count; SJC = swollen joint count; CRP = C-reactive protein in mg/L; ESR = erythrocyte sedimentation rate in mm/first hour, PtGA = subject's global assessment of health; PhyGA = physician's global assessment of health, HAQ-DI = Health Assessment Disability Questionnaire-Disability Index; LDA = Low Disease Activity. RAPID3 = Routine Assessment of Patient Index Data 3.

Appendix 1.2. Definition and Use of Visit Windows in Reporting

Visit windows will be used for efficacy variables, and for any safety displays that display by week.

If more than one observation from the same subject falls into the same visit window, the value closest to the targeted day will be used as the observation for that week. If two visits are equal distant from the Targeted Day in absolute value, the later visit should be used. All observations will, however, be included in the listings.

For endpoints derived from multiple components, eg, DAS28-4(ESR), each component will be windowed to select the value for analysis at a specific visit, and the value of the endpoint will then be derived. This means the component values may be from different visit dates that fall within the analysis window.

Subjects’ observations will be excluded from visit windows if the data was collected more than 7 days off study drug. (Safety analysis may follow Pfizer standard.)

Visit Label	Targeted Day	Analysis window for data sets
Open-Label Run-In Phase		
Baseline	Day 1	Last Observation up to and including First Dosing Date (no earlier than Day -90)
Week 6	Day 42	Days 2 – 63
Week 12	Day 84	If there is Week 6 visit such as lab tests: Days 64 – 126; If no Week 6 visit: Days 2 – 126
Week 24	Day 168	Day 127 – Discontinuation Day /Randomization Day (the earlier one)
Double-Blind Phase		
Randomization (Week 24)	Randomization Day	Last Observation up to and including First Dosing Date in Double-Blind Phase (no earlier than Day 127)
Week 36	Randomization Day + 84	Randomization Day + 1 – Randomization Day + 126
Week 48	Randomization Day + 168	Randomization Day + 127 –
